2.1.2.2. BMT CTN 1301 (CNI-Free)

BMT CTN 1301 study is a three arm randomized Phase III, multicenter trial comparing two calcineurin inhibitor (CNI)-free strategies for GVHD prophylaxis to standard calcineurin inhibitor tacrolimus and methotrexate (Tac/Mtx) in patients with acute leukemia or myelodysplasia undergoing myeloablative conditioning hematopoietic stem cell transplantation. The primary objective of the randomized trial is to compare chronic GVHD/relapse-free survival [CRFS] as a time to event endpoint after hematopoietic stem cell transplant (HSCT) between each of the CNI-free interventions and a Tac/Mtx control. Secondary objectives are: comparison of rates of grade II-IV and III-IV acute GVHD, chronic GVHD, chronic GVHD-free survival, immunosuppression-free survival at one year, neutrophil and platelet engraftment, disease relapse, transplant-related mortality, rates of Grade ≥ 3 toxicity; incidence of CMV and EBV reactivation, incidence of infections, immune reconstitution, quality of life and overall survival.

2.1.3. Rationale for Study Design

These BMT CTN multicenter clinical trials were selected based on their total accrual goal and current enrollment rates to use as a platform to conduct this randomized study. These trials were chosen to reflect common indications and/or complications of HCT and the diversity and complexity of transplant technologies and supportive care treatments. Random allocation to the two study arms will reduce selection bias and will ensure that socio-demographic factors (including education status and health literacy levels) and disease characteristics of patients are comparable. There is a potential that patients, if aware that they are on the ETRIC arm, may overestimate their comprehension and satisfaction scores and underestimate their anxiety levels.

2.1.4. Hypothesis and Study Objectives

The primary hypothesis is that the patients consenting using the ETRIC form will have higher levels of comprehension of BMT CTN transplant protocols and risks associated with participation in the trial compared to patients consented using standard consent forms. The secondary hypotheses are that patients using the ETRIC forms will have lower anxiety and greater satisfaction with the consent process.

2.1.4.1. Primary Objective

The primary objective of the study is to determine whether the ETRIC form increases patient comprehension of informed consent compared to the standard consent form for the BMT CTN

parent studies. This will be achieved by comparing patient comprehension scores on the Quality of Informed Consent (QuIC) Part A instrument between patients randomized to the two arms.

2.1.4.2. Secondary Objectives

The secondary objectives are to compare additional measures of comprehension and measures of patient anxiety, satisfaction, and information location between the two arms. Specifically, these will include subjective comprehension scores on the QuIC (Part B) instrument, comprehension scores on the modified Deaconess Informed Consent Comprehension Test (DICCT), state anxiety scores on the State Trait Anxiety Inventory (STAI), satisfaction scores, and time taken for information location. The study will also explore patient consent rates on parent clinical trials for the two arms.

2.1.5. Patient Eligibility Criteria

Inclusion and exclusion criteria for the ETRIC randomized study will be the same as the eligibility criteria for the BMT CTN parent studies. Additional inclusion criterion specific for the ETRIC study will include:

1. Adult patients (≥ 18 years).
2. Speaking and reading proficiency in English (as most of this study's instruments have not been translated and validated in languages other than English).
3. Willing and able to provide informed consent.
4. Stated willingness to comply with study procedures and reporting requirements.

2.1.6. Study Interventions

Patients will be randomized to either the ETRIC arm or the standard consent arm. The ETRIC consent form was developed by NMDP's Patient Services department, which has expertise in health literacy and in development of consent documents for clinical trials, in consultation with clinical trial protocol team. The ETRIC form has a two-column format with specific attention towards enhancing readability and processability including layout, organization of content, typography, and using plain language (Section 1.2). The standard consent form has a single column format and lacks the formatting and readability enhancements of the ETRIC form. For patients randomized to the standard consent arm, participating centers will be allowed to use the standard consent form they are presently using for consenting patients for the parent studies. The content of both forms are similar and both contain all federally required elements for informed consent. Individual clinical trial sites will be allowed to make modifications to the ETRIC and the standard consent forms to meet requirements of their local IRBs. The BMT CTN 1205 protocol team will ensure that any such modifications to the ETRIC form conform to the easy-to-read format.

2.1.7. Hematopoietic Cell Transplantation

The BMT CTN 1205 study is a non-therapeutic ancillary study. Patients will receive HCT and/or its associated treatments and supportive care as outlined in the BMT CTN parent protocols. In the event that a patient does not consent for participation in the BMT CTN parent trial, he/she will receive standard HCT and/or its associated treatments as recommended by his/her treating physician.

2.1.8. Study Risks and Benefits

Risks of study participation are expected to be minimal. Similarly, the study interventions are not expected to impact clinical outcomes. It is unknown whether study participants will experience any benefits.

2.1.9. Study Withdrawal

Subjects may be withdrawn from study participation if the treating physician believes it is in the patient's best interest.

2.2. Evaluation Study

2.2.1. Study Overview

For the evaluation study, site visits will be scheduled to 9 transplant centers to understand barriers to the implementation of the ETRIC form. This will include visits to 5centers that are participating in the randomized consent form study as well as another 4 trial sites that are not participating in the consent study but are enrolling patients on the BMT CTN parent clinical trials. This approach will provide us with a wide spectrum of procedures related to the consent process that are followed by trial sites and their IRBs.

At each site, we will conduct semi-structured interviews of IRB administrators, site protocol investigators, and study coordinators. Semi-structured interviews will last 30-45 minutes and will examine: (1) willingness to utilize and acceptability of ETRIC two-column format, (2) perceived barriers to implementation, (3) previous experience with alternative format informed consent forms or novel methods of obtaining consent, (4) perception of value of ETRIC, and (5) helpfulness of resources provided to facilitate implementation of ETRIC (e.g., quick reference resources for design and format elements, template with default settings for format and design, additional resources for design support, educational resources for IRB and protocol team members, BMT CTN recommendations).

Qualitative analyses will be conducted to identify themes representing facilitators and barriers to the local implementation of the ETRIC form. Other methods to conduct interviews (e.g., telephone interviews) were considered. However, face-to-face interviews have certain advantages. First, high unit and item response rates, valid data and detailed information can be captured by face-to-face interviews because longer interviews can be conducted and support can be provided by interviewers as they observe non-verbal expressions of respondents.^{35,36} Also, we would like the interview participant to give feedback on specific elements of the ETRIC form

which would be easier with the face-to-face interview than a telephone interview given the length of the consent forms and range of familiarity with the ETRIC form.

2.2.2. Center Selection Criteria

All centers participating in the BMT CTN parent clinical trials will be eligible to participate in the evaluation study. The BMT CTN 1205 (ETRIC) study protocol team will invite centers to participate in this study based on center interest and accrual rates on the parent BMT CTN clinical trials.

CHAPTER 3

3. STUDY ENDPOINTS

3.1. Study Endpoints for Randomized Study

The instruments that will be used for study assessments are described in Section 4.4.

3.1.1. Primary Endpoint

The primary endpoint objective of this study is to compare objective comprehension scores on the QuIC Part A instrument between patients randomized to the ETRIC and the standard consent arms.

3.1.2. Secondary Endpoints

The secondary endpoints will compare the following measures between the two arms: (1) subjective comprehension scores on the QuIC (part B) instrument and the modified DICCT instrument, (2) state anxiety scores on STAI instrument, (3) satisfaction scores, (4) time taken for information location, and (5) patient consent rates on parent clinical trials.

3.2. Study Endpoints for Evaluation Study

[figure not shown]
For the evaluation study, using qualitative research methods (semi-structured interviews), the study will determine: (1) willingness to utilize and acceptability of ETRIC two-column format, (2) perceived barriers to implementation, (3) previous experience with alternative format informed consent forms or novel methods of obtaining consent, (4) perception of value of ETRIC, and (5) helpfulness of resources provided to facilitate implementation of ETRIC (e.g., quick reference resources for design and format elements, template with default settings for format and design, additional resources for design support, educational resources for IRB and protocol team members, BMT CTN recommendations).

CHAPTER 4

4. PATIENT REGISTRATION AND ENROLLMENT FOR RANDOMIZED STUDY

4.1. Approaching Patients, Eligibility Screening and Obtaining Consent

Subjects may be approached for enrollment on the ETRIC protocol once they have been identified as potential participants for the BMT CTN 1101 or 1301 studies. Note that the BMT CTN 0901 trial and BMT CTN 1203 trial were removed as parent trials due to their closure on April 18, 2014 and May 13, 2016, respectively, and no further patients will be enrolled from these studies. The following scenarios regarding eligibility/participation in the ETRIC study can occur (Figure 4-1):

Figure 4-1. Possible Scenarios for Patient Registration

- 1) Scenario 1: On patient assessment, he/she is not found to be eligible for the parent trial. In this case, the patient would not be approached for participation in the BMT CTN 1205 (ETRIC) randomized study. He/she will proceed with HCT or other treatments as recommended by his/her physician.
- 2) Scenario 2: On patient assessment, he/she is found to be potentially eligible for the parent trial. However, on approaching the patient for the study, he/she indicates no interest in participation or going through the consent process. He/she will proceed with HCT or other treatments as recommended by his/her physician.
- 3) Scenario 3: On patient assessment, he/she is found to be potentially eligible for the parent trial and is interested in proceeding with the consent process for the study. Once patient expresses interest in the parent study, he/she will be approached for participating in the

BMT CTN 1205 (ETRIC) study. In this case, patient declines participation in the BMT CTN 1205 (ETRIC) study, and he/she will proceed with the consent process for the parent trial using their standard consent form.

- 4) Scenario 4: On patient assessment, he/she is found to be potentially eligible for the parent trial and is interested in proceeding with the consent process for the study. Once patient expresses interest in the parent study, he/she will be approached for participating in the BMT CTN 1205 (ETRIC) study. In this case, patient agrees to participate in the BMT CTN 1205 (ETRIC) study. He/she will be randomized and will undergo consent discussions for the parent study using either the ETRIC or the standard consent forms.

In case a patient consents to and is enrolled on the BMT CTN 1205 (ETRIC) study, and then subsequently is found to not meet the eligibility criteria for the parent study (prior to the consent discussion for the study), he/she will be removed from the BMT CTN 1205 (ETRIC) study (this situation would be similar to Scenario 1 above). No ETRIC assessments will be conducted for such patients.

Patients who agree to participate in the BMT CTN 1205 (ETRIC) study, and then go through the consent process for but decline participation in or are later found ineligible for the parent study, will continue on the BMT CTN 1205 (ETRIC) study. They will be asked to complete all the assessments for the BMT CTN 1205 (ETRIC) study even though they do not proceed onto the parent study.

Transplant physicians or other center staff will evaluate patient eligibility for enrollment for the BMT CTN 1205 (ETRIC) study. Eligibility criteria will be verified and ineligible patients will proceed off study and no further study procedures will be conducted. Eligible patients willing to potentially participate in the BMT CTN 1205 (ETRIC) study will have a thorough discussion about the protocol with an investigator, a sub-investigator, clinical research nurse, or research coordinator. If necessary, this discussion may take place by telephone. During the discussion, the purpose of the study and study procedures will be presented as objectively as possible, and the potential benefits and risks of participation will be explained. Patients will be registered through EMMES AdvantageEDCSM (Electronic Data Capture, an Internet-based data entry system).

4.2. Study Registration and Randomization

Once the subject is deemed eligible, has given informed consent, and the transplant center has confirmed patient eligibility, randomization occurs. A subject may be randomized on to one of two arms: ETRIC vs. standard consent.

4.3. Consent

Given the number of consents and randomization conversations subjects will encounter, the randomized portion of the ETRIC study will seek a waiver of the requirement to document consent from the IRBs of participating sites according to the requirements of the Common Rule (Section 46.117(c)(2)) (also see Appendix A). This does not mean that informed consent will not occur but rather that informed consent process will be verbal and subjects will neither read nor sign an informed consent form. Specific items will still need to be addressed in the consent

conversation as required by the federal regulations, as shown in the consent script (Appendix D). Subjects will be given a written information sheet about the BMT CTN 1205 (ETRIC) study that addresses all required elements of informed consent (Appendix E). Additionally, a sample letter to the participating site's IRB requesting a waiver from the requirement to document consent is attached as Appendix C. The Principal Investigator or his/her designee at each transplant center will contact the candidates to enroll them onto the study. The study coordinator at each center will provide the patient with information about the purpose of the study and obtain verbal consent, either in person or over the phone. The date of verbal consent will be recorded and saved in the patient's study file.

4.4. Patient Assessment

4.4.1. Study Assessments

Table 4-4-1 describes the patient reported assessments that will occur as part of the BMT CTN 1205 (ETRIC) study. All assessments will occur at one time – within 7 business days of consent discussion for the parent trial. These assessments will be conducted in addition to other assessments being performed for the parent trials and any other ancillary studies in which the patient might be participating. (Note, there are no patient reported assessments for the 1203 trial.)

Table 4-4-1: Summary of Study Assessments

| Instrument | Description | Administration |
|---|--|------------------------------|
| Health Literacy | | |
| - Rapid Estimate of Adult Literacy in Medicine (REALM) ³⁷ | Medical-word recognition and pronunciation test comprising 11 medical terms, arranged in order of complexity by the number of syllables and pronunciation difficulty; scores assigns health literacy skills into 4 categories of grade-equivalent reading level | Study coordinator, 2 minutes |
| - Newest Vital Sign (NVS) ³⁸ | Measures health literacy level using 1 scenario of an ice cream container nutrition label; 1 score (6 items) includes assessment of two main constructs, numeracy and reading comprehension | Study coordinator, 3 minutes |
| Comprehension | | |
| - Quality of Informed Consent (QuIC) ⁴ | Measures subjects actual (objective - part A, 16 items) and perceived (subjective - part B, 14 items) understanding of cancer clinical trials to address 13 independent domains of informed consent; responses measured in a 3 item (part A) or 5 item (part B) Likert scale | Self administered, 7 minutes |
| - Modified Deaconess Informed Consent Comprehension Test (DICCT) ³⁹⁻⁴¹ | Semi-structured interviews assess subjects understanding of 8 core elements of disclosure for the study they have agreed to participate in. Scores of 2,1 or 0 are assigned to responses that indicate complete, partial or no understanding of each element. | Study coordinator, 5 minutes |
| Anxiety | | |
| - State Trait Anxiety Inventory (STAI) ⁴² | Measures anxiety and distinguishes it from depressive syndromes; 40 items to assess state/trait anxiety; responses rated on a 4 point Likert scale | Self administered, 5 minutes |
| Satisfaction | | |
| - Study specific and QuIC Supplement ⁴³ | Short study specific questionnaire and selected questions from the QuIC supplement questionnaire will query participants about their overall satisfaction with the consent process, helpfulness of information provided, and comprehension of key study-specific elements of treatment | Self administered, 5 minutes |
| Information location | | |
| - Study specific | Participants will be asked to identify 5 items of information within the consent document; time taken to locate items will be measured | Study coordinator, 5 minutes |

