Anxiety related to the consent process will be measured using the State Trait Anxiety Inventory (STAI), a commonly used and validated tool with good internal consistency, test-retest reliability.⁴² There are no validated instruments for measuring satisfaction with the informed consent process. A short questionnaire that can be self-administered by patients will be developed to measure satisfaction and understanding of key study-specific elements. In addition, selected questions will be used from the QuIC supplement to assess satisfaction.⁴³ There are no validated instruments for measuring consent information location (text search ability). To measure information location and to differentiate it from comprehension, the time it takes for subjects to locate 5 important items of information in the consent form will be determined.

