5.5. Analysis Plan

The primary analysis will be performed using the intention-to-treat principle so that all randomized patients will be included in the analysis. The t-test or the Mann-Whitney test will be used if the t-test assumptions are violated. Secondary endpoints of subjective comprehension, anxiety, satisfaction, and information location will be analyzed with the Mann-Whitney test. The binary outcome of consent rates will be compared using the Fisher exact test. The above unadjusted analyses will be complemented by analyses that adjust for potentially confounding

variables in regression analyses. Generalized estimating equations (GEE)⁵⁰ will be used to control for effect of confounding variables (e.g., patient demographics, health literacy level, strata) and a potential consenter effect (as more than one clinician could be involved in the consent process at a clinical trial site). GEE with identity link will be used for comprehension, anxiety and satisfaction analyses. Information location will be analyzed with LOG link and LOGIT link with accrual outcome. Variance will be estimated with the sandwich estimator if the number of consenters is > 30; otherwise the “leave-one-consenter-out” jackknife variance estimation will be used.⁵¹ Exact logistic regression will be used with accrual if the problem of small counts appears. Otherwise Wald tests will be used for significance testing. All two-way interactions between the group indicator (ETRIC vs. standard) and confounding variables will be tested and added to the model if significant. It is expected that all confounders will be analyzed as fixed effects except for the consenter which will be the repeated factor in the GEE. The form of continuous predictors will be either linear, quadratic, or categorized depending on the number of clusters observed in the dataset. Every category in categorical variables will have at least 10 subjects otherwise we will consider merging with neighboring categories. The presence of missing data in excess of 10% will be addressed by developing an imputation model for missing components given the observed part. Then, the multiple imputations approach will be used to estimate regression parameters and their standard errors.⁵²

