Data preparation: We will investigate functional forms of continuous predictor variables, such as "literacy level" (assessed via NVS or REALM-R) and "age" and the use of appropriate transformations of continuous predictors to make the associations with the outcome more linear and the distributions of model residuals closer to normal. We will also consider grouping continuous variables into three categories by tertiles if the linear association with the outcomes is not adequate. The categories of variables with multiple levels, such as "Education level" or "Income", will be grouped into wider categories.

The adjusted analysis of the primary endpoint will be based on the linear regression model. Potential confounding variables to include in the model are (1) the trial protocol, (2) literacy level (NVS or REALM-R, whichever is more predictive), (3) income, (4) gender, (5) age, (6) categorized race (WHITE vs OTHER). Forward stepwise variable selection will be used to find a parsimonious linear regression model with significant at ALPHA = 5% predictors.

Missing data: Since only near two thirds of all study participants are expected to complete the Quality of Informed Consent (Part A) questionnaire, we will develop an imputation model and use multiple imputations to fill-in missing values. The imputation model will use the information at baseline when the participant is enrolled into the study. Then, we will use Little and Rubin's approach (Little & Rubin, 2002) to combine the results of multiple imputations for estimating model parameters, variance covariance matrices, and P-values. To investigate the possibility of missing data which are not missing at random (NMAR), we will use tipping-point

NCT02081248

approach and find the ranges of the imputation model parameters when the inference on the effect of ETRIC consent does not change.

Dependence within data: The linear mixed models will be used to explore whether there is a need to control for clinical trial site or clinical trial site by protocol, both or neither.

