Alternative analyses: To satisfy model assumptions we will consider the use of monotone variance-stabilizing transformations for continuous variables. If, however, the model specification continuous being inadequate (non-Gaussian distribution of model residuals, outliers, etc.), we proceed with generalized estimating equations (GEE) instead of the mean linear regression. To accommodate potential dependence of responses within clinical trial sites “leave-one-site-out” cross-validation will be used to estimate robust standard errors of the test statistic (the regression coefficient of the ETRIC effect in either mean or median regression models).

Secondary Endpoints and Final Analysis:

Secondary continuous endpoints are subjective comprehension, anxiety, satisfaction, and information location. The only secondary binary endpoint is the consent rate for the parent clinical trial.

Analysis of secondary endpoints: By analogy with the primary endpoint, the secondary endpoints (1) subjective comprehension scores on the Quality of Informed Consent (part B) instrument, (2) the modified Deaconess Informed Consent Comprehension Test instrument, (3) state anxiety scores on State Trait Anxiety Inventory instrument, (4) overall satisfaction score will be analyzed using t- or Mann-Whitney tests as appropriate. The analysis of time to information location will be performed with generalized linear models (GLM) models using the LOG link function if nonlinearity needs to be accounted for. The comparison of consent rates between ETRIC and standard consent forms will be performed with GEE using the LOGIT link. The GEE model will control for the fixed effect of trial protocol and for the dependence within the clinical trial site. The statistical significance of the ETRIC intervention on each of the secondary endpoints will be declared if the P-values of two-sided Wald test with robust standard errors <0.05. Missing data will be treated by analogy with the primary outcome using multiple imputations and tipping-point analysis.

Patients to Include:

All patients who completed the Quality of Informed Consent (part A) survey will be included in the primary data analysis. All enrolled patients will be included in the data analysis of secondary endpoints.

Content of Tables

Tables:

Table 1: Demographics and baseline characteristics by treatment arm

Table 2: Study endpoints by treatment arm

Table 3: Interaction analyses for the Quality of Informed Consent (part A)

NCT02081248

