Table 4: Adjusted analysis of Quality of Informed Consent (part A) instrument

Figures:

Figure 1: CONSORT diagram (a separate file is attached for a template)

Figure 2: Bar graphs of means and standard errors for the primary and secondary endpoints in ETRIC and Standard consent forms (below is an example).

[figure not shown]

Table 1: Demographics and baseline characteristics by treatment arm

	Treatment Arm		P-value
	ETRIC N(%) or N(M+/-SE)	Standard N(%) or N(M+/-SE)	
Gender			
- Female (N)			
- Male (N)			
Hispanic/Latino			
- Yes (N)			
- No (N)			
- Missing (N)			
Race			
- White (N)			
- Black (N)			
- Other (N)			
- Missing (N)			

NCT02081248

The Trial Protocol			
- BMT CTN 0901 (N)			
- BMT CTN 1101 (N)			
- BMT CTN 1203 (N)			
- BMT CTN 1301 (N)			
Income (\$)			
- <20,000 (N)			
- 20,000-39,999 (N)			
- 40,000-59,999 (N)			
- 60,000-79,999 (N)			
- 80,000-99,999 (N)			
- 100,000+ (N)			
- Missing (N)			
Age (years)			
Education Level			
- Education Group 1 (N)			
- Education Group 2 (N)			
- Education Group 3 (N)			
- ...			
- Missing (N)			

Table 2: Study endpoints by treatment arm

	Treatment Arm		
	ETRIC N(%) or N(M+/-SE)	Standard N(%) or N(M+/-SE)	P-value
Quality of Informed Consent (part A)*			
Quality of Informed Consent (part B)			
Modified Deaconess Informed Consent Comprehension Test			
The State Trait Anxiety Inventory Score			
Overall Satisfaction Survey			
Averaged Time to Information Location (sec)			
- Where can you find the main goal of the study?			
- Where can you find who to contact if you have questions about the study?			
- Where can you find the risks to taking part in the study			
- Where can you find how to leave the study?			
- Where can you find what you will have to do in the study?			
Consent Rate of Parent clinical Trial (Y/N)			

NCT02081248

 - BMT CTN 0901 (N) - BMT CTN 1101 (N) - BMT CTN 1203 (N) - BMT CTN 1301 (N) 			
--	--	--	--

*primary outcome

Table 3: Interaction analyses for the Quality of Informed Consent (part A)

	Treatment Arm		
	ETRIC (N) M +/-SE	Standard (N) M +/-SE	P-value
The Trial Protocol			

 - BMT CTN 0901 (N) - BMT CTN 1101 (N) - BMT CTN 1203 (N) - BMT CTN 1301 (N) 			
Literacy level (REALM-R)			

 - Missing (N) 			
Income (\$)			

 - <20,000 (N) - 20,000-39,999 (N) - 40,000-59,999 (N) - 60,000-79,999 (N) - 80,000-99,999 (N) - 100,000+ (N) - Missing (N) 			

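### Information location is scored only as time, with no rule for an item the patient never finds; if such items are left blank, the arm comparison may be biased, in a direction set by which form has more failures.

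*Protocol*

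**What the plan says.** Table 4-4-1 of the protocol (section 4.4.1) describes the task: "Participants will be asked to identify 5 items of information within the consent document; time taken to locate items will be measured". The coordinator administers it, and the table lists 5 minutes for it. Section 4.4.2 notes that no validated instrument exists for this construct and defines the measure again as a time: "the time it takes for subjects to locate 5 important items of information in the consent form will be determined".

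SAP Table 2 has a row labelled "Averaged Time to Information Location (sec" and one row for each of the five search questions. It has no row for the number or share of items located. The SAP's list of instrument scoring rules covers the QuIC, REALM-R, NVS, STAI, satisfaction survey and DICCT, but not information location.

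On analysis, protocol section 5.5 says: "Secondary endpoints of subjective comprehension, anxiety, satisfaction, and information location will be analyzed with the Mann-Whitney test". It adds a GEE with log link for adjustment. The later SAP says: "The analysis of time to information location will be performed with generalized linear models (GLM) models using the LOG link function", where nonlinearity calls for it.

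On absent values of secondary endpoints, the SAP says: "Missing data will be treated by analogy with the primary outcome using multiple imputations and tipping-point analysis". For the primary outcome it says: "The imputation model will use the information at baseline when the participant is enrolled into the study". It gives the purpose of the second component as follows: "To investigate the possibility of missing data which are not missing at random (NMAR), we will use tipping-point".

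**The concern.** A patient who gives up on an item, is stopped, or points to the wrong place has produced a result, and it is a poor one. A variable that holds only seconds-to-locate has no place for that result. Someone must then decide whether to leave the cell blank, enter the time at which the search ended, or average the remaining items. The documents do not decide it, so coordinators at different centers may do different things.

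If the cell is left blank, the plan offers two routes. Averaging the items that were found gives the patient a mean built only from successful searches. Imputing from baseline information draws a time from a model that does not know the search failed. Either way, a poor search can be given an ordinary time.

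The endpoint matters to the trial's argument. Protocol section 1.2 justifies the two-column layout partly by saying that it helps readers locate information, and this is the only measure that tests that directly.

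**Working it through.** **What the documents supply.** They give no effect size, standard deviation, failure rate, time limit or power for this endpoint, so there is no planned figure to reproduce. The sample size in protocol section 5.2 (64 per group, then 74, then 198 in total) is for QuIC Part A and does not depend on this point. All times, spreads and stopping times below are assumptions.

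**Step 1: direction of the bias.** Let *a* and *b* be the mean times of found items for ETRIC and standard, *p1* and *p0* the shares not found, and *c* the value given to an unfound item.

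- Found items only: difference = *b* − *a*
- Unfound items scored at *c*: difference = [(1 − *p0*)*b* + *p0c*] − [(1 − *p1*)*a* + *p1c*]

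Assume found times are lognormal with medians 20 s and 25 s and log-SD 0.5, truncated at *c* = 60 s. Then *a* = 21.95 s and *b* = 26.40 s, and the found-only difference is 4.4 s whatever the failure rates.

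| Not found, ETRIC / standard | Found only (s) | Scored at 60 s (s) |
|---|---|---|
| 0% / 0% | 4.4 | 4.4 |
| 10% / 10% | 4.4 | 4.0 |
| 5% / 10% | 4.4 | 5.9 |
| 5% / 20% | 4.4 | 9.3 |
| 10% / 5% | 4.4 | 2.3 |
| 20% / 5% | 4.4 | −1.5 |

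For the third row: (0.90 × 26.40 + 0.10 × 60) − (0.95 × 21.95 + 0.05 × 60) = 29.76 − 23.86 = 5.9 s. Leaving failures out understates the difference when the standard form has clearly more of them. It overstates the difference, or hides a reversal, when ETRIC has more.

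**Step 2: size when one latent time drives both speed and failure.** Assume lognormal item times, patient SD 0.4 and item SD 0.7 on the log scale, medians 30 s (ETRIC) and 40 s (standard), and an item unfound if its time exceeds a per-item stop. The total log-SD is √(0.16 + 0.49) = 0.806. The share not found is 1 − Φ(ln(stop/median)/0.806). At 60 s:

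- standard: 1 − Φ(0.405/0.806) = 31%
- ETRIC: 1 − Φ(0.693/0.806) = 20%

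The power figures are simulated, two-sided at 5%, with 66 per arm. That number is two thirds of 99, borrowed from the completion the SAP expects for QuIC Part A; this coordinator-run task may do better.

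| Assumed stop per item | Not found, ETRIC / standard | Mann-Whitney power, found items only | Power, unfound scored at the stop |
|---|---|---|---|
| 60 s | 20% / 31% | 63% | about 85% |
| 120 s | 4% / 9% | 82% | 87% |
| 180 s | 1% / 3% | 85% | 87% |

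At 60 s the ratio of found-only means is 0.88, against a true ratio of 30/40 = 0.75.

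**Step 3: sensitivity to search speed.** Take a second model with medians 20 and 25 s, log-SD 0.7, within-patient correlation 0.5 and a 60 s stop. About 6% and 10% of items are unfound. Power is 57% on found items, 60% with unfound items scored at the stop, and 32% if any patient with an unfound item is dropped altogether. With equal medians (25 s each) there was no bias.

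**What was not computed.** These runs drop unfound items; none performs the SAP's multiple imputation. Baseline-only imputation would recover the loss only as far as baseline data predict a failed search.

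**The case against.** Several stronger readings are tempting, and the documents do not support them.

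- **That failed searches become missing data.** No section says so. The task is run by a coordinator, who might record the time at which the search stopped or let it run until the item is found. The collection form is not in the documents and may hold a not-found code. This part stands: the bias is conditional on how failures were recorded.
- **That absent values are simply imputed as missing at random.** The SAP also applies a tipping-point analysis to secondary endpoints, aimed at data not missing at random. That is a real provision. It is a sensitivity check, however: it leaves the main estimate as it was and does not separate an item not found from a task not attempted.
- **That the arm difference shrinks.** Step 1 shows this needs more failures with the standard form, and that the opposite is possible.
- **That 5 minutes for five items means a 60 s limit.** The figure stands in the administration column beside the times for the other instruments; it is an expected duration. If it is read as a limit on the whole task, under the step 2 model, found-only against complete-time power is 84% against 87% (medians 30/40 s), 86% against 86% (22.5/30 s) and 76% against 85% (45/60 s). The loss is large mainly with a short per-item stop or slow searches.
- **That a quick wrong answer scores well.** The protocol times how long it takes to locate items, and a wrong place is arguably not a location. What can be said is that neither document states how correctness is judged.

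The simulations also use the protocol's Mann-Whitney test, whereas the SAP plans a GLM for this endpoint.

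**Conclusion.** The gap is real. The endpoint is a time only, with no limit, no found/not-found record and no scoring rule. The plan's rule for absent values cannot distinguish a failed search from an undone task. Whether this biases the result depends on failures having been left blank, which the documents do not show. The direction depends on which form produces more failures.

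The size cannot be derived from the documents. Under the assumptions in step 2, the power loss is about 22 percentage points with a 60 s stop per item (63% against 85%), 5 at 120 s and 2 at 180 s. The point deserves a change because the remedy is cheap and better than time-only scoring, and because a failure that was never recorded cannot be recovered at analysis. It concerns one secondary endpoint.

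**What to change.** **For the data already collected.** The SAP puts the close of enrollment in August 2016, before its own draft date, so a new form field cannot help this trial. Before analysis, state in the SAP how items not located, or located wrongly, are identified from the existing forms. Give them the worst rank when forming the patient's score, and compare arms by the Mann-Whitney test of protocol section 5.5 in place of the GLM. State that an unlocated item is an observed outcome, and keep multiple imputation and the tipping-point analysis for tasks not attempted. Add a row to SAP Table 2 for items located (0 to 5) by arm. If the forms do not show which items failed, say so when reporting the endpoint.

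**For any later use of the task.** Record for each item whether it was correctly located and the time taken. Set one common stopping time, and score unlocated or wrongly located items at that cap.

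**Cost.** A few SAP sentences and one table row now; one yes/no box per item in a future form. The downside is that the mean in seconds becomes a capped time, or gives way to a rank comparison, and is less direct to interpret.
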